**Table 1. Cohort Definitions**

Name	Criteria	Identification Period	Index Date	Follow Up Period
Treated patients	Patients diagnosed with COVID-19 and treated with Paxlovid™	After Paxlovid™ availability during the same dominant variant (ie, Omicron or Delta etc.) era timeframe as Cohort	Paxlovid™ prescription written date or dispense date*  If neither of the above are available, the COVID-19 diagnosis date may be used as the index date	28 -days follow up
Control group	Patients diagnosed with COVID-19 and not treated with Paxlovid™	After Paxlovid™ availability during the same dominant variant (ie, Omicron or Delta etc.) era timeframe as Cohort	Date of COVID-19 diagnosis	28 -days follow up

\*If both dates are available in the data source, the most recent date should be used as the index date for Cohort.

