#### **9.4. Data Sources**

There is a database of all patients who were eligible for Paxlovid™ therapy and details of those that accepted Paxlovid™ therapy and those that did not. Between 16 February 2022 and 30 November 2022, there were 8263 patients that met all study inclusion and exclusion criteria eligible for Paxlovid™ therapy of whom at least 3000 patients were treated with Paxlovid™ therapy and 1000 were not. All records from the participant cohort of 8263 will be reviewed.

Data on these patients that were treated with Paxlovid™ therapy and those that did not will be extracted from the I-Seha Electronic Health Record (EHR). I-Seha EHR will be used to collect the variables listed below including: medical, biochemical and pharmacy data, HER data, and patient registry data. The I-Seha EHR data contains unstructured data that will be anonymized. I-Seha uses a large, geographically diverse administrative claims dataset which comprises patients served by a number of different health systems, providers and benefit structures. Complete information regarding all healthcare utilization submitted for payment is included in database.

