**Table 4. HRU Data**

Variable	Operational definition
Hospital Length of Stay	The total length of stay (LOS) recorded for all hospitalizations during the baseline period and follow-up period in days (excluding within 24 hours of Paxlovid™ initiation).
ICU/Non-ICU LOS	The total number of days in the intensive care unit (ICU) and the number of days that were not spent in the ICU (non-ICU) recorded for all hospitalizations during the baseline period and follow-up period in days (excluding within 24 hours of Paxlovid™ initiation).
IMV/No IMV LOS	The total number of days with and without invasive mechanical ventilation (IMV) recorded for all hospitalizations during the baseline period and follow-up period in days (excluding within 24 hours of Paxlovid™ initiation).
Hospitalizations (Count and Percentage)	The count and percentage of patients with all-cause and COVID-related hospitalizations (excluding within 24 hours of Paxlovid™ initiation) during the baseline and follow-up period.
Number of Hospitalizations per Patient	The number of hospitalizations per patient in the baseline and follow-up periods for all-cause and COVID-related hospitalizations (excluding within 24 hours of Paxlovid™ initiation) will be described.
Number of Hospitalizations per Patient among Patients with Readmissions	The number of all-cause and COVID-related hospitalizations (excluding within 24 hours of Paxlovid™ initiation) per patient in the baseline and follow-up periods will be described among patients with readmissions during the same period. The cause for readmission will be reported when available.
Time to First Outpatient Encounter	Time from COVID-19 diagnosis to the earliest outpatient encounter to occur after diagnosis during the baseline period.

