**Table 5. COVID-19 Disease Outcome Variables**

Variable	Operational definition
ICU Admission	Patients with ICU admission during COVID-related hospitalizations in the baseline and follow-up periods (excluding within 24 hours of Paxlovid™ initiation).
IMV Usage	Distribution of patients with IMV (ie, intubation and mechanical ventilation) usage, including extracorporeal membrane oxygenation (ECMO), during COVID-related hospitalizations in the baseline and follow-up periods (excluding within 24 hours of Paxlovid™ initiation).
Supplemental Oxygen Usage	Distribution of patients with supplemental oxygen usage during COVID-related hospitalizations in the baseline and follow-up periods (excluding within 24 hours of Paxlovid™ initiation).
Non-invasive Ventilation Usage	Distribution of patients with non-invasive ventilation usage during COVID-related hospitalizations in the baseline and follow-up periods (excluding within 24 hours of Paxlovid™ initiation).
High-flow Nasal Cannula Usage	Distribution of patients with high-flow nasal cannula usage during COVID-related hospitalizations in the baseline and follow-up periods (excluding within 24 hours of Paxlovid™ initiation).
Hospital Discharge Status	Distribution of patient discharge status for COVID-related hospitalizations during the baseline and follow-up periods (excluding within 24 hours of Paxlovid™ initiation). Discharge status should include transfer to skilled nursing facility, transfer to another healthcare facility, home, expired (dead), transfer to other long-term care facility, transfer to hospice based on the values recorded in the database.
Time from COVID-19 Test to Paxlovid™ Treatment	Time from the earliest COVID-19 test in the baseline period to the earliest date of Paxlovid™ prescription written date AND dispense date.
COVID-19 Lab Tests with Positive Result	The count and percentage of patients with a COVID-19 lab test with a positive result during the baseline and follow-up periods will be reported.
COVID-19 Lab Test with Variant Type	When available, the count and percentage of patients with each COVID-19 variant of concern (VOC) during the baseline period will be reported.
Monoclonal Antibody Usage	Patients with monoclonal antibody usage during the baseline and follow-up periods. Monoclonal antibody usage will include tocilizumab and bamlanivimab/etesevimab.

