## 1.1 STUDY DESIGN

This study is a retrospective cohort study examining COVID-19 patients who were treated with Paxlovid. It will also include a control group of COVID-19 patients who were offered, but refused, Paxlovid. It will involve a secondary data analysis of patient data from the ISeha electronic medical records.

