**Table 4: COVID-19 disease outcome variables**

Variable	Operational definition
Hospitalizations	Number of all-cause and COVID-related hospitalizations (excluding within 24 hours of Paxlovid initiation) during the baseline and follow-up period per patient
Number of Hospitalizations per Patient	The number of hospitalizations per patient in the baseline and follow-up periods for all-cause and COVID-related hospitalizations (excluding within 24 hours of Paxlovid initiation)
Number of Hospitalizations per Patient among Patients with Readmissions	The number of all-cause and COVID-related hospitalizations (excluding within 24 hours of Paxlovid initiation) per patient in the baseline and follow-up periods will be described among patients with readmissions during the same period. The cause for readmission will be reported when available.
Time to First Outpatient Encounter	Time from COVID-19 diagnosis to the earliest outpatient encounter to occur after diagnosis during the baseline period.

PFIZER CONFIDENTIAL

Hospital Length of Stay	The total length of stay (LOS) recorded for all hospitalizations during the baseline period and follow-up period in days (excluding within 24 hours of Paxlovid initiation)
ICU/Non-ICU LOS	The total number of days in the intensive care unit (ICU) and the number of days that were not spent in the ICU (non-ICU) recorded for all hospitalizations during the baseline period and follow-up period in days (excluding within 24 hours of Paxlovid initiation)
IMV/No IMV LOS	The total number of days with and without invasive mechanical ventilation (IMV) recorded for all hospitalizations during the baseline period and follow-up period in days (excluding within 24 hours of Paxlovid initiation)
ICU Admission	ICU admission during COVID-related hospitalizations in the baseline and follow-up periods (excluding within 24 hours of Paxlovid initiation)
IMV Usage	IMV (i.e., intubation and mechanical ventilation) usage, including extracorporeal membrane oxygenation (ECMO), during COVID-related hospitalizations in the baseline and follow-up periods (excluding within 24 hours of Paxlovid initiation)
Supplemental Oxygen Usage	supplemental oxygen usage during COVID-related hospitalizations in the baseline and follow-up periods (excluding within 24 hours of Paxlovid initiation)

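### The 24-hour exclusion can remove only treated patients' events, and day 0 differs by group, so the HRU comparison can show a difference with no drug effect

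*Protocol*

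**What the plan says.** **Day 0.** Protocol Table 1 indexes treated patients at the prescription or dispense date and adds: "If both dates are available in the data source, the most recent date should be used as the index date for Cohort". If both are missing: "If neither of the above are available, the COVID-19 diagnosis date may be used as the index date". The control index is "Date of COVID-19 diagnosis". Each group is followed for 28 days from its own index. The SAP gives no start date for counting controls' resource use. It ties only the symptom telephone call to prescription.

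**24-hour rule.** Protocol Table 4 counts "COVID-related hospitalizations (excluding within 24 hours of Paxlovid™ initiation) during the baseline and follow-up period". The same parenthesis is attached to length of stay (total, ICU, IMV) and, in Table 5, to ICU admission, IMV, oxygen, non-invasive ventilation, high-flow cannula and discharge status. SAP Table 4 repeats it: "Number of all-cause and COVID-related hospitalizations (excluding within 24 hours of Paxlovid initiation) during the baseline and follow-up period per patient". Neither document gives controls an equivalent date or rule. Death (protocol Table 3, SAP Table 2) carries no 24-hour rule and is counted from an enrollment date.

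**Who the controls are.** Protocol 9.1 and Table 1 describe any COVID-19 patient not treated with Paxlovid. Protocol 9.4 describes a database of eligible patients with "details of those that accepted Paxlovid™ therapy and those that did not". SAP 1.1 is narrower: "It will also include a control group of COVID-19 patients who were offered, but refused, Paxlovid".

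**Use.** Protocol 9.1 commits to comparing resource use between the groups. SAP 1.12 and 1.13 plan inferential tests of disease outcomes at alpha 0.05 with 95% confidence intervals, and the SAP Table 7 shell has P-value and effect-size columns.

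**The concern.** An outcome definition that can delete events in one group only is not the same outcome in both groups. If some admissions fall in the first 24 hours after initiation, treated patients lose them and controls keep theirs. Separately, two 28-day windows that start at different points in the illness cover different stretches of risk.

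Either feature can move the contrast with no drug effect. The propensity-score list in SAP 1.13 has no timing variable. Matching on patient characteristics could not in any case repair an outcome that is defined differently by group. At stake is the secondary objective on resource use and outcomes.

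**Working it through.** The plan states no effect size or power for this comparison, so there is no figure to reproduce. The check asks what risk ratio (RR, treated over control) the rules give with no drug effect.

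**Inputs from the documents:** 3000 treated and 1000 controls (protocol 9.5); 3% hospitalization risk, moderate-risk group, and 6% as the high-risk alternative (protocol 9.7); alpha 0.05; horizons of 28 days (protocol) and five days (SAP objective iv).

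**Assumptions, not in the documents:** 3% applies over 28 days; lag L from diagnosis to prescription is 0, 1 or 2 days, equal to the controls' lag to the offer; initiation equals index; only follow-up events are counted; tests are two-sided pooled z-tests; five admission-time curves as listed below.

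**Formulas.** F(d) = R × G(d)/G(28), where R is the 28-day risk and G the cumulative distribution of time from diagnosis to admission. With horizon H:

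- Treated, no 24-hour rule: [F(L+H) − F(L)] / [1 − F(L)]
- Treated, with the rule: [F(L+H) − F(L+1)] / [1 − F(L)]
- Control, refuser unadmitted at the offer but counted from diagnosis: [F(H) − F(L)] / [1 − F(L)]
- Control, any untreated patient counted from diagnosis: F(H)

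**Worked cell** (exponential, mean 5 days, L = 0, H = 28). G(1) = 0.1813 and G(28) = 0.9963, so F(1) = 0.03 × 0.1813/0.9963 = 0.00546. Treated risk is 0.03 − 0.00546 = 0.02454, and RR = 0.02454/0.03 = 0.818. The rule removes 3000 × 0.00546 = 16.4 of 90 expected treated admissions. A 5% test then rejects in 16.9%.

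**28-day null RR at 3%, refuser controls, lags 0/1/2:**

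| Admission timing | 24-hour rule alone | Index mismatch alone | Both |
|---|---|---|---|
| Exponential, mean 5 | 0.818 / 0.818 / 0.818 | 1.000 / 1.001 / 1.002 | 0.818 / 0.819 / 0.820 |
| Exponential, mean 10 | 0.899 / 0.899 / 0.899 | 1.000 / 1.007 / 1.015 | 0.899 / 0.905 / 0.912 |
| Gamma, peak day 4 | 0.986 / 0.933 / 0.879 | 1.000 / 1.000 / 1.000 | 0.986 / 0.933 / 0.880 |
| Gamma, peak day 6 | 0.998 / 0.983 / 0.952 | 1.000 / 1.000 / 1.000 | 0.998 / 0.983 / 0.953 |
| Constant rate | 0.964 / 0.964 / 0.964 | 1.000 / 1.037 / 1.077 | 0.964 / 1.000 / 1.038 |

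With both rules, rejection runs from 5.0% to 16.9% at 3% risk and reaches 28.1% at 6%.

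**If controls are any untreated patient.** With mean 5 and L = 2, the index mismatch alone gives 0.0203/0.03 = 0.68, and both rules give 0.0166/0.03 = 0.55. At a constant rate the mismatch alone stays at about 1.00.

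**Five days, refuser controls.** The 24-hour rule alone gives 0.71 to 0.99, the index mismatch alone 1.00 to 1.99, and both together 0.71 to 1.78.

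**If one row pools the baseline year.** Assume a prior-year admission risk q, equal in both groups, and take the worst 28-day cell. At q = 5%: [1 − 0.95 × 0.97546]/[1 − 0.95 × 0.97] = 0.0733/0.0785 = 0.93. At q = 10%: 0.1221/0.1270 = 0.96.

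**If matching is 1:1 on 1000 controls.** Worst-case rejection falls from 16.9% to 11.6%, and at 6% risk from 28.1% to 18.9%.

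**The case against.** The study is called descriptive and the tests exploratory. The SAP marks hypotheses and decision rules as not applicable, and protocol 9.9 disclaims causality. That limits the weight, and the primary baseline objective is largely untouched. It does not remove the defect: the groups are still tested on these outcomes, and a rule that differs by group distorts the association itself, not only its causal reading.

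The size is fragile, and this stands. RR 0.82 needs the admission hazard to be highest at diagnosis; later-peaking or constant curves mostly sit near 1. The variables are worded to cover baseline as well as follow-up, and SAP Table 7 has no period split, so a pooled row would dilute the effect. The SAP does not state the matching ratio, and 1:1 matching lowers the rejection rate.

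Offered-but-refused, outpatient controls make the groups more alike, but they supply neither a common day 0 nor a 24-hour rule for controls.

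Two stronger readings are tempting. A reader might infer that both rules favour Paxlovid. The documents do not support that: with refusers unadmitted at the offer, the event-free days before the offer use up part of the control window, so the index mismatch pushes the other way. A reader might also infer that treated patients indexed at diagnosis have no initiation date. Table 1 says only that prescription and dispense dates are unavailable, and initiation is not defined. The supportable statement is that the plan does not say how the 24-hour rule applies to them.

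**Conclusion.** The point holds as a defect in the current text. The 24-hour exclusion can remove only treated patients' events, day 0 differs by group, and nothing in either document corrects this. The resource-use comparison can therefore show a difference with no drug effect.

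Under the stated assumptions the 24-hour rule alone gives a 28-day null RR of 0.82 to 1.00; pooling an assumed 5–10% prior-year admission risk shrinks 0.82 to 0.93–0.96. The index mismatch has no settled direction: 1.00 to 1.08 at 28 days with refuser controls, and below 1 with any-untreated controls when admissions come early. At five days the direction of the combined effect is undetermined. Confidence is high in the asymmetry of the text and low in any single figure, because lag and admission timing are assumed. It should be fixed before analysis; it concerns a secondary objective.

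**What to change.** 1. In protocol Tables 4 and 5 and SAP Table 4, state the 24-hour exclusion relative to the index date in both groups, or drop it in both. Run the other choice as a sensitivity analysis.
2. In protocol Table 1 and the SAP, use one type of day 0 and the same horizon for both groups: the offer date if recorded, otherwise a common landmark or a pseudo-index for controls, chosen by the sponsor. Count only patients alive and unadmitted on that date.
3. Report outcome counts after day 0 separately from the baseline year.
4. Count death from the same day 0 (protocol Table 3, SAP Table 2).
5. Reconcile the control definition (protocol 9.1 and Table 1 against SAP 1.1 and Study population) at the same time, because it sets the direction of the index-date bias.

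Items 1 and 2 are both needed. With refuser controls, fixing only day 0 leaves RR 0.82–1.00 at 28 days. Fixing only the 24-hour rule leaves 1.00–1.08 at 28 days and 1.00–1.99 at five days. With both fixed, the null RR is 1 by construction in this model. Confounding between those who accepted and those who refused remains.

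The cost is a protocol amendment (Tables 1, 3, 4, 5) with matching SAP edits (Tables 2 and 4, Table 7 shell), and edits to the statements in protocol 9.2.2 and the SAP that there are no exclusion criteria. Prescription and dispense dates must be kept as separate fields, since protocol Table 2 and SAP Table 1 now keep only the later one. The offer date may need extraction, and a few early control events are lost.

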## 9.2. Setting

### 9.2.1. Inclusion Criteria

- Patients must meet all of the following inclusion criteria to be eligible for inclusion in the study: Age 18 years and older
- Patients with a diagnosis of COVID-19 whose information can be extracted from the I-Seha database

### 9.2.2. Exclusion Criteria

**There are no exclusion criteria for this study.**

## 9.3 Variables

The following variables are used to obtain comprehensive descriptive results.

1. Demographics
2. Date of symptoms
3. Viral variant analysis where available (type of viral variant ie, omicron, delta etc.)
4. PCR date along with CT Value

5. Co-morbidities and
6. BMI if  $\geq 30$
7. Symptoms at presentation
8. COVID 19 vaccine status (NB 92% of population has been vaccinated -with at least one dose of COVID 19 vaccine- in Bahrain)
9. Hospital admission
10. Follow up looking at compliance and reason of non-compliance
11. Day 5,7, 21 and 28 symptoms for COVID-19 patients who receive and HRU limited to admission (ICU, ward, need for oxygen therapy) or death
12. Date of symptoms resolution if applicable

**Table 2** Table 2 below depicts the patient demographics that will be accessed during the baseline and follow-up periods. The baseline period is defined as one year before the index date. Comorbidities (full list in [Table 6](#)) and maintenance medication usage for chronic conditions (eg, statins, antihypertensives, etc.) will be described during the baseline period and follow-up periods and are listed in [Table 3](#).

Risk factors for severe COVID-19, intensive care unit (ICU) usage, invasive mechanical ventilation (IMV) usage, supplemental oxygen use, non-invasive ventilation, and high-flow nasal cannula usage are depicted in [Table 5](#) and will be extracted from the *I-Seha* national electronic health record database.

Where applicable, emerging treatment patterns may be assessed as the time from symptom onset to COVID-19 diagnosis, time from symptom onset to treatment initiation, and the time from COVID-19 diagnosis to treatment initiation as illustrated in [Table 5](#).

10Nov23 WHO recommendations for Paxlovid treatments to define: 1. COVID-19 patients who meet the WHO criteria for “strongly recommended” 2. COVID-19 patients who meet the WHO criteria for “conditionally recommended”, and 3. COVID patients who are not falling into categories 1 or 2 will be used.

#### **9.4. Data Sources**

There is a database of all patients who were eligible for Paxlovid™ therapy and details of those that accepted Paxlovid™ therapy and those that did not. Between 16 February 2022 and 30 November 2022, there were 8263 patients that met all study inclusion and exclusion criteria eligible for Paxlovid™ therapy of whom at least 3000 patients were treated with Paxlovid™ therapy and 1000 were not. All records from the participant cohort of 8263 will be reviewed.

Data on these patients that were treated with Paxlovid™ therapy and those that did not will be extracted from the I-Seha Electronic Health Record (EHR). I-Seha EHR will be used to collect the variables listed below including: medical, biochemical and pharmacy data, HER data, and patient registry data. The I-Seha EHR data contains unstructured data that will be anonymized. I-Seha uses a large, geographically diverse administrative claims dataset which comprises patients served by a number of different health systems, providers and benefit structures. Complete information regarding all healthcare utilization submitted for payment is included in database.

#### 9.4.1. EHR Database

There is a database of all patients who were eligible for Paxlovid™ therapy and details of those that accepted Paxlovid™ therapy and those that did not. Data on these patients that were treated with Paxlovid™ therapy and those that did not will be extracted from the I-Seha EHR. A retrospective review will be undertaken of patients symptom database to discern patient-reported symptoms (eg, time from onset, duration, severity, frequency) will be described in this study. Following Paxlovid™ treatment initiation, patients were followed up by a telephone call, regarding their symptom onset and severity; review of this standard of care data will be used to complement emerging treatment patterns and clinical characteristics throughout this study. For those that did not take Paxlovid™ treatment, data will be extracted by the CRAs from the EHR on patient reevaluation in a healthcare facility, admission to hospital or death.

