### Inferential statistics

Between-group differences in categorical variables will be examined using proportions tests, Chi-square tests of independence or Fisher exact tests as appropriate. Differences in continuous variables will be examined using independent t-tests.

Differences in proportions or means (as appropriate) and 95% confidence intervals between COVID-19 patients taking Paxlovid, and COVID-19 patients who were offered Paxlovid therapy but who refused treatment will be reported. Additionally, Cramer's V or Cohen's d will be reported.

Cramer's V is a measure of association that quantifies the strength and direction of the relationship between the two categorical variables being compared. Cramer's V ranges from 0 to 1, where 0 indicates no association between the variables, and 1 represents a perfect association. The magnitude of Cramer's V will be interpreted as follows:

Cramer's V	Effect Size
-------------------	--------------------

0.1	Weak
0.3	Medium
0.6	Large

Cohen's d quantifies the standardized difference between the means of the two groups, and is calculated by taking the difference between the means of the two groups and dividing it by the pooled standard deviation. The magnitude of Cohen's d will be interpreted as follows:

Cohen's d	Effect Size
------------------	--------------------

0.2	Small
0.5	Medium
0.8	Large

An a priori alpha level of 0.05 has been selected for all tests. As this work is exploratory no adjustment for multiple comparisons will be made.

PFIZER CONFIDENTIAL

CT24-WI-GL03-RF03 2.0 *Non-Interventional Statistical Analysis Plan For Secondary Data Collection*  
Study 01-Jun-2020  
Page 14 of 22

Selection of the control groups will consider the following characteristics based on the availability of data using propensity-score matched:

- age,
- sex,
- COVID vaccination status,
- high-risk status for severe COVID-19 outcomes (WHO definition),
- assessment of healthcare seeking behavior in 365 days prior to COVID infection (such as flu or streptococcus pneumoniae vaccine, has primary healthcare provider, number of primary care/hospital visits),
- socioeconomic factors (such as household income, employment status),
- geographic location of residence,
- comorbidities.

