**Table 6: Descriptive statistics for clinical characteristics**

Variables	Group		P-value	Effect size
	Paxlovid	Control		
Patient-reported Covid-19 symptoms, % (n)				
Stuffy or runny nose				
Sore throat				
Shortness of Breath				
Cough				
Low energy/Tiredness/fatigue				
Muscle ache/body aches				
Headache				
Chills or shivering				
Feeling hot/feverish				
Nausea or vomiting				
Diarrhea				
Loss of sense of smell				
Loss of sense of taste				
Comorbidities (ICD-10)				
Vaccination Status, % (n)				
Completely				

PFIZER CONFIDENTIAL

CT24-WI-GL03-RF03 2.0 *Non-Interventional Statistical Analysis Plan For Secondary Data Collection Study* 01-Jun-2020  
 Page 18 of 22

Partially				
Unvaccinated				
Risk factors for severe Covid-19, % (n)				
Age $\geq$ 50 years				
Obesity (BMI $\geq$ 35)				
Chronic kidney disease (eGFR $\geq$ 30 ml/min)				
Diabetes Mellitus				
Primary and Secondary Immunosuppressive disease or immunosuppressive treatment				
Cardiovascular disease (including congenital heart disease) or hypertension				
Chronic lung diseases (for example, chronic obstructive pulmonary disease, asthma [moderate-to-severe], interstitial lung disease, cystic fibrosis, and pulmonary hypertension)				
Sickle cell disease				
Neurodevelopmental disorders				
Having a medical-related technological dependence (for example, tracheostomy, gastrostomy, or positive pressure ventilation [not related to COVID-19])				
Death, % (n)				
Inpatient death, % (n)				

PFIZER CONFIDENTIAL

CT24-WI-GL03-RF03 2.0 *Non-Interventional Statistical Analysis Plan For Secondary Data Collection Study* 01-Jun-2020  
 Page 19 of 22

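### The SAP propensity list has no measure of illness at presentation, although presenting symptoms and onset date are listed for extraction, so outcomes in accepters and refusers are compared without balancing it

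*Protocol*

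**What the plan says.** **What is collected.** Protocol 9.3 lists "Symptoms at presentation", the date of symptoms and "PCR date along with CT Value". Protocol Table 2 (variables at index) names 13 symptoms and a symptom onset date. SAP Table 2 repeats the 13 symptoms and SAP Table 1 keeps the onset date. Protocol 9.4.1 adds that "patient-reported symptoms (eg, time from onset, duration, severity, frequency) will be described in this study", without a time point or a scale for severity.

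**When severity is recorded, and for whom.** The only severity record with a stated time is in Protocol 9.4.1: after treatment began, "patients were followed up by a telephone call, regarding their symptom onset and severity". For untreated patients the same section says "data will be extracted by the CRAs from the EHR on patient reevaluation in a healthcare facility, admission to hospital or death".

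**What is balanced.** SAP 1.13 states: "Selection of the control groups will consider the following characteristics based on the availability of data using propensity-score matched". The list that follows is age, sex, vaccination status, "high-risk status for severe COVID-19 outcomes (WHO definition"), care seeking, socioeconomic factors, location and comorbidities. The covariate section (SAP 1.11) is marked not applicable.

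**What is compared.** Controls were offered the drug and refused it (SAP 1.1). SAP 1.12 applies inferential statistics to disease outcomes in the two groups. SAP 1.13 names proportions, chi-square, Fisher and t-tests, with 95% confidence intervals and an alpha of 0.05. The SAP Table 7 shell has p-value columns for hospitalisation, ICU admission, ventilation and oxygen. The SAP Table 6 shell shows "Patient-reported Covid-19 symptoms, % (n") by group, also with a p-value and an effect size.

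**The concern.** The control group is formed by the patient's own decision. How ill a patient feels when the offer is made can plausibly affect both that decision and the later chance of admission, oxygen or ICU care. A variable that affects both is a confounder, and the propensity list is the only confounding control in the plan.

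A perfect match on the eight listed items would still leave presenting illness unbalanced, except as far as it correlates with them. Two patients of the same age, vaccination status and comorbidities can present with a runny nose or with breathlessness. If SAP Table 6 showed such an imbalance, nothing in the planned analysis of SAP Table 7 would correct for it.

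The effect could go either way. If sicker patients accept more often, the drug looks worse than it is. If sicker patients refuse more often, it looks better.

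**Working it through.** **Step 1: text check.** Each candidate measure of illness at presentation was compared with the propensity list.

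| Measure | Listed for extraction | In the SAP variable tables | In the propensity list |
|---|---|---|---|
| 13 presenting symptoms | Yes (Protocol 9.3, Table 2) | Yes (SAP Table 2) | No |
| Symptom onset date | Yes (Protocol 9.3, Table 2) | Yes (SAP Table 1) | No |
| CT value | Yes (Protocol 9.3) | No | No |
| Severity grade at presentation | Not established | No | No |

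The WHO groups are defined in both documents by immunosuppression, age and chronic conditions. They give the risk of later severe disease, not current illness.

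**Step 2: possible size of the bias.** The plan has no figure of its own to reproduce, so this is an illustration. Only the group sizes of about 3000 and 1000 come from the plan (SAP 1.5). The other inputs are assumptions:
- share with moderate illness: a = 0.50 in accepters; b = 0.30 or 0.40 in refusers;
- admission risk ratio for moderate against mild illness: R = 2, 3 or 4;
- control admission risk: 3% or 6%, borrowed from the WHO moderate-risk and high-risk groups;
- no drug effect.

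Spurious risk ratio = (1 + a(R − 1)) / (1 + b(R − 1)).

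- b = 0.30: R = 2 gives 1.5/1.3 = 1.15; R = 3 gives 2.0/1.6 = 1.25; R = 4 gives 2.5/1.9 = 1.32.
- b = 0.40: R = 2 gives 1.5/1.4 = 1.07; R = 4 gives 2.5/2.2 = 1.14.
- Reversed (a = 0.30, b = 0.50): R = 2 gives 1.3/1.5 = 0.87; R = 4 gives 1.9/2.5 = 0.76.

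**Step 3: chance of a false p<0.05.** The test is the pooled two-proportion (chi-square) test, two-sided at 0.05. Let d be the difference in risk, s0 its pooled standard error and s1 its unpooled standard error. The rejection probability is Φ((d − 1.96·s0)/s1) + Φ((−d − 1.96·s0)/s1).

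Example with b = 0.30, R = 4, control risk 3%, 3000 against 1000:
- accepter risk = 0.03 × 1.316 = 0.0395, so d = 0.0095;
- pooled risk = (3000 × 0.0395 + 1000 × 0.03)/4000 = 0.0371;
- s0 = 0.00690 and s1 = 0.00646;
- (0.0095 − 0.0135)/0.00646 = −0.63, so the probability is about 0.27. The second term is negligible.

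| Illness split | Group sizes | Control risk 3% | Control risk 6% |
|---|---|---|---|
| 50% vs 30%, R 2 to 4 | 3000 vs 1000 | 10 to 27% | 16 to 51% |
| 50% vs 30%, R 2 to 4 | 1000 vs 1000 | 9 to 21% | 13 to 38% |
| 50% vs 40%, R 2 to 4 | 3000 vs 1000 | 6 to 9% | 7 to 14% |

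The 1000 vs 1000 row assumes 1:1 matching. The SAP gives no matching ratio and does not say whether the tests are run in the matched set.

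**The case against.** **The study is descriptive.** The SAP states no hypotheses, calls the work exploratory, and Protocol 9.9 disclaims causality. This limits what may be concluded. It does not remove the point, because Protocol 9.1 says healthcare use will be compared, and the SAP attaches p-values and confidence intervals to outcomes and chooses to match. The limitation in 9.9 is generic and does not name presenting illness.

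**The range of illness is narrow and an imbalance would be visible.** The clinic targets mild to moderate disease (Protocol section 7), patients were managed as outpatients, and SAP Table 6 reports the 13 symptoms by group. This stands in part: restriction reduces the possible bias but does not balance what remains. The Table 6 rows also carry no time point, so they would show a baseline imbalance only if they hold presenting symptoms.

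**The stronger reading.** A reader might infer that severity was graded at presentation and then dropped from the SAP. The documents do not support this. Protocol 9.4.1 mentions severity without a time point, the only timed severity record is the call after treatment began, and Protocol Table 2 defines the variable by the same 13 symptoms as the SAP.

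**The data may be thin in refusers.** This stands. For untreated patients, Protocol 9.4.1 names only re-evaluation, admission or death. If presenting symptoms are missing mainly in refusers, a *not recorded* category would largely identify the treatment group, damage overlap and lose matches without removing confounding.

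**Conclusion.** The omission is confirmed on the text. Symptoms at presentation and onset date are listed for extraction, the propensity list contains no measure of illness at presentation, and the outcome tests adjust for nothing else. It should be corrected before analysis.

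The size is uncertain. A 20-point imbalance in moderate illness gives a spurious risk ratio of 1.15 to 1.32, and a false-positive rate two to five times nominal at 3% control admission. A 10-point imbalance gives 1.07 to 1.14 and a rate close to nominal. If refusers are the more ill, the bias favours the drug. The prevalences and risk ratios are assumed, as is the premise that current illness affects acceptance.

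The 3% and 6% should not be read as this study's admission rates in controls. Both are WHO estimates for generic risk groups, and neither document gives a control-group rate.

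**What to change.** In SAP 1.13, add to the propensity list presenting illness dated on or before index:
- shortness of breath (yes/no);
- number of the 13 listed symptoms present;
- days from symptom onset. Count these to diagnosis in both groups, because Protocol Table 1 sets index at prescription or dispensing for treated patients and at diagnosis for controls;
- a severity grade only if it was recorded before index in both groups.

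State that symptoms from the telephone call after treatment began are not used as baseline. Label the symptom rows in SAP Table 6 as presenting symptoms. Report completeness of these items by group, and standardised differences after matching. State that the outcome tests are run in the matched set.

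Use a *not recorded* category only if missingness is similar in the two groups. If presenting data are missing mainly in refusers, run the match with these covariates as a sensitivity analysis among patients with records, and name residual confounding by presenting illness as a limitation.

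The cost is SAP wording and a few derived variables from items already listed for extraction, with no new data source. The downside is some loss of matches and incomplete symptom records in refusers.
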